6.9 Concomitant Medications

With the exception of medications listed as prohibited (see below, this section), enrolled study participants may use concomitant medications during study participation. All concomitant medications, including prescribed and over-the-counter preparations, vitamins and nutritional supplements, recreational drugs and herbal preparations reported within 45 days prior to confirmation of eligibility for study enrollment and throughout the course of the study will be recorded on the CRF designated for that purpose. Medications used for the treatment of AEs that occur during study participation will also be recorded on applicable study CRFs. Participants who begin taking any medication during the trial that is listed as an exclusionary medication at Screening will temporarily discontinue study drug. Study drug may be resumed if no exclusionary medication has been taken in the last 4 weeks, if serum creatinine is within 1.3-fold above baseline, and if HIV testing is non-reactive/negative.

Should participants report use of any of the following medications, they will be required to discontinue use of study drug: interleukin therapy, medications with significant nephrotoxic potential (including but not limited to amphotericin B, aminoglycosides, cidofovir, foscarnet and systemic chemotherapy), and medications that may inhibit or compete for elimination via active renal tubular secretion (including but not limited to probenecid).

7.0 STATISTICAL CONSIDERATIONS

7.1 Review of Study Design

This is an open-label, three-site, prospective, uncontrolled demonstration project that aims to assess the initiation, acceptability, safety, and feasibility of daily PrEP for BMSM in three U.S. cities utilizing C4 models. HIV-uninfected BMSM aged 18 and over and at risk for HIV infection will be recruited and enrolled. Each participant will be offered daily PrEP and followed up to 52 weeks. Participants will be followed at the specified study time points and will be evaluated for side effects, renal toxicity, adherence, risk behavior and HIV-seroconversion.

Primary Endpoints: The primary endpoints of this study are the initiation of and adherence to PrEP.

Initiation of PrEP

The timing of initiation of PrEP and correlates will be documented in either study CRFs or ACASI. A manual will be created for all sites to follow when introducing PrEP to participants based on safety and efficacy language found in the ICF under "Study Purpose".

Adherence to PrEP

Adherence will be assessed via self-report (ACASI), PBMCs and plasma concentration. Specifically, biological assessments of adherence will be objectively measured by obtaining plasma, and lysed PBMCs at specified study visits. Plasma will be assayed for TFV and FTC. PBMC will be assayed for TFV-DP and FTC-TP. Assay results will be compared to best available standards (e.g., results from directly observed dosing study results like STRAND or HPTN 066) to estimate level of adherence. Plasma and PBMC will be compared. A detailed analytical plan such as Bland-Altman plots and kappa statistics to measure concordance/discordance between different measures of PrEP adherence will be developed in a separate analysis plan.

Secondary Endpoints: The secondary endpoints of this study include the following:

Sexual risk-taking behavior

Sexual risk-taking behaviors will be measured by ACASI assessments performed at baseline and then at follow-up visits.

Reasons BMSM choose to initiate or refuse PrEP

Refusal rates will be measured by ACASI assessments conducted at enrollment and follow-up visits, which will be supplemented by acquiring information about core reasons for initiating or refusing PrEP, based on the individual interview qualitative data from participants.

Incident HIV-seroconversions and characteristics

HIV testing will be performed with confirmation if necessary at all study visits per procedures outlined in the SSP. HIV RNA and genotyping will be performed at the NL on samples confirmed to be HIV infected.

Adverse events

Measurement of AEs will be graded via the DAIDS Toxicity Grading System determined by review of reported adverse events (clinical and laboratory) during the study.

Sexually transmitted infections (STIs)

STIs will be measured at baseline, monthly for the first three months and then at quarterly visits. Tests will include rectal and urine GC/CT, and NAAT for syphilis and chlamydia.

Participant perception of care and referral plans

Participant Perception of care and referral will be assessed via interviewer-administered questionnaire at Weeks 13, 26, 39 and 52.

Exploratory endpoints:

Dried Blood Spots Assessment

To assess PrEP adherence via DBS assessment of study drug and anabolite concentrations for TFV, FTC, FTC-TP and TFV-DP using semi-quantitative methods, and to compare it with adherence measured by drug concentrations in plasma and PBMC. Semi-quantitative methods will be used given the lack of known precision of the current DBS analytical methods and present/not present interpretations may be needed. Use of DBS testing for off-study ARV drug use may also be explored.

ARV Testing using a Multi-drug Screening Assay

Stored plasma samples will also be tested using a high-throughput multi-drug ARV screening assay. Results from this assay will be compared to other Pharmacologic assessments of adherence, and to assess off study ARV drug use.

Cost Characterization

Since the intervention may provide good value for the money spent (e.g., the cost of a vaccine vs. the cost of treating those who are infected), cost characterization will be described regarding space and staff needs for administering PrEP.

7.2 Sample Size Consideration

A total sample size of 225 BMSM participants will be recruited into the study. Each participant will be enrolled to receive C4 and offered daily PrEP for at least 12 months.

According to the primary objective, two primary endpoints are considered: (1) PrEP initiation measured by the acceptance rate of the BMSM who are offered PrEP, and (2) PrEP adherence measured by the percentage of PrEP adherence among the BMSM who choose PrEP.

For the PrEP initiation endpoint, Table 3 lists the two-sided 95% confidence intervals for the true percentage of the PrEP acceptance rate for the BMSM who are offered PrEP. For example, if the observed PrEP acceptance rate is 50%, then there is 95% chance that the range of 44% - 57% will contain the true PrEP acceptance rate.

Table 2: 95% Confidence Intervals for the True PrEP Initiation Given by Possibly Observed PrEP Percentages

Ν	Observed PrEP Acceptance Rate	95% CI for True PrEP Acceptance Rate
	33%	(27%, 39%)
225	50%	(44%, 57%)
	67%	(61%, 73%)

For the PrEP adherence endpoint, Table 4 lists the two-sided 95% confidence intervals for the true percentage of the PrEP adherence rates for the BMSM who actually receive PrEP, assuming a 10% to 20% loss-to-follow-up (e.g. including those lost due to incarceration) during the 12-month period. For example, if the PrEP acceptance rate is 50% and an observed adherence rate is 67%, then there is 95% chance that the range 58%-76% will contain the true PrEP adherence rate.

Table 3:95% Confidence Intervals for the True PrEP Adherence Rate Given by Possibly
Observed PrEP Adherence Percentages

PrEP Acceptance Rate	PrEP Adherence Rate	95% CI for True PrEP Adherence Rate
----------------------	---------------------	--

		10% LTFP*	20%LTFP*
	33%	(22%, 44%)	(21%, 45%)
33% (low)	50%	(38%, 62%)	(37%, 63%)
	67%	(56%, 78%)	(55%,79%)
	33%	(24%, 42%)	(23%, 43%)
50% (moderate)	50%	(40%, 60%)	(39%, 60%)
	67%	(58%, 76%)	(57%,77%)
67% (optimistic)	33%	(25%, 41%)	(25%,41%)
	50%	(42%, 58%)	(41%,59%)
	67%	(59%, 75%)	(59%.75%)

*LTFP: Loss-to-Follow-up

7.3 Data Analysis

7.3.1 Primary Analyses

- To assess initiation and adherence of daily PrEP among BMSM who are offered PrEP. PrEP acceptability will be assessed by the acceptance/refusal rate of PrEP. PrEP initiation will be measured by time-to-PrEP initiation. The measure of initiation can be a participant's use of PrEP at any point in the study. Acceptance and refusal rates will be calculated, with 95% exact or normally approximated binomial confidence intervals. Acceptance and refusal rates will also be calculated by age, education, site, and risk practices. In addition, to identify correlates associated with refusal, we will use backward stepwise multivariate logistic regression models to examine statistically significant factors. Predictiveness of associated factors will be summarized by respected ROC curves. Kaplan-Meier plots will be used to characterize time to PrEP initiation, overall and by age, education, and risk group.
- To assess adherence and persistence to PrEP among participants in the demonstration project. • PrEP persistence time is defined as the time from PrEP start to PrEP discontinuation. A PrEP discontinuation is considered to have occurred if a participant self-reported via ACASI to miss the PrEP doses for 30 or more consecutive days, for reasons other than a medication hold instituted by a clinician.. Kaplan-Meier plots will be used to characterize time to first discontinuation, as well as time to restarting PrEP among discontinuers, both overall and by age, education, and risk group. Among those continuing on treatment, we will consider the so-called medication possession ratio, defined as the number of tablets dispensed divided by the number of days between visits, a measure that performed best as an indicator of drug exposure in the iPrEx study. Adherence patterns of interest (e.g., intermittent use only before planned exposures) will also be assessed by self-report, and their prevalence characterized by reporting period. Tablet-taking practices will also be evaluated by drug detection rates in biological samples. Concordance between quantitative adherence measures based on self-report and pharmacological measures will be assessed using Bland-Altman plots; concordance of binary measures of drug detection will be assessed using the Kappa statistic. PrEP persistence times will be analyzed by multiplicative Andersen-Gill counting processes models.

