3.2.1 Vulnerable Populations

Persons under 18 years of age will not be included as the effects of ARV therapy on physical development and other growth parameters (e.g., effects on bone growth and bone mineral density) in HIV-uninfected children and minors have not been fully evaluated, and exploration of these safety issues is beyond the scope of this project.

Incarcerated persons will not be screened or enrolled into this study due to logistical, technical, and ethical reasons. Based on data collected in HPTN 061, a substantial proportion of participants are expected to become incarcerated over the duration of follow up. Incident incarcerations will be reported to each site's Institutional Review Board (IRB. Information known about the incarcerated will be systematically collected on study case report forms (CRFs). Participants who are incarcerated

once they are enrolled in the study will not be followed while incarcerated, no data will be collected on them, and neither C4 nor PrEP provided. However, once released, participants will be followed, if they wish, from the time of release until the originally scheduled Week 52 visit.

As individuals who are incarcerated will not be available for study procedures, staff members typically learn of their incarceration via procedures implemented when unable to reach participants for a scheduled clinic visit. Each study site will develop their own SOPs for locating participants via friends, family, public electronic databases of incarcerated individuals.

Approximately 15-30 participants or 10% to 20% are anticipated to become incarcerated at some point during follow-up. This information is based on HPTN 061 recruitment and its' study population. Incarceration includes jail, prison, etc. which would prevent men from attending any study follow-up visits.

Any person who cannot provide informed consent will be excluded from participation in the project. Staff conducting screening will be trained to identify participants who cannot provide appropriate informed consent. If it is determined that the inability to provide informed consent is due to a temporary/situational factor (e.g., intoxication), these persons will be given the opportunity to reschedule their enrollment appointment as appropriate. All participants will be afforded the same protections.

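### PrEP persistence tends to be overstated because discontinuation is recognised only through ACASI, so a man with no later ACASI cannot register a gap that starts after his last visit

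*Protocol*

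**What the plan says.** Section 7.3.1 states that "PrEP persistence time is defined as the time from PrEP start to PrEP discontinuation". A discontinuation occurs "if a participant self-reported via ACASI to miss the PrEP doses for 30 or more consecutive days", provided the gap is "for reasons other than a medication hold instituted by a clinician". No other trigger and no other exception is given. The same section says "Kaplan-Meier plots will be used to characterize time to first discontinuation", overall and by age, education and risk group, and it applies Andersen-Gill models to persistence times.

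After enrollment, ACASI is scheduled at Weeks 13, 26, 39 and 52 (Sections 5.5 and 5.6, Appendix IA). Study product is supplied at study visits, with no supply at Week 52 (Appendix IA, footnote 5).

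For men in custody, Section 3.2.1 says "no data will be collected on them, and neither C4 nor PrEP provided", but also that "once released, participants will be followed, if they wish, from the time of release until the originally scheduled Week 52 visit". It expects the following: "Approximately 15-30 participants or 10% to 20% are anticipated to become incarcerated at some point during follow-up". Section 7.2 computes the adherence intervals "assuming a 10% to 20% loss-to-follow-up (e.g. including those lost due to incarceration) during the 12-month period".

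**The concern.** The event can be observed only in men who come back to report it. A man who stops attending also stops being supplied, so the process that removes him from observation is tied to the outcome being measured. Kaplan-Meier and Andersen-Gill both need censoring to be unrelated to the later risk of the event, and that is doubtful here.

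Persistence is part of the primary analyses of adherence in Section 7.3.1. An upward bias would make PrEP use look more durable than it was. If loss differs by age, education or risk group, the comparison of curves between those groups is affected as well as their level. The medication possession ratio in the same section does not fill the gap, because it is restricted to men who continue on treatment.

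**Working it through.** **1. Who is affected**

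- Lost with no further visit: no later ACASI and no later supply. A gap that starts after the last visit is never recorded.
- Incarcerated and not returning: the same, and the protocol itself says no PrEP is provided.
- Incarcerated, released and returning before Week 52: the gap can be reported. A stay under 30 days need not be a discontinuation.
- Leaving with an exit evaluation (Sections 3.5 and 5.8): a gap that already exists can be reported, but not one that begins at exit.

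The problem is therefore confined to men with no later ACASI.

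**2. The plan's own figures**

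The adherence intervals in Table 3 follow p ± 1.96 × √(p(1 − p)/n), with n = 225 × acceptance × (1 − loss). For 50% acceptance and 67% adherence:

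- 10% loss: n = 101, giving 57.8% to 76.2% (stated 58% to 76%).
- 20% loss: n = 90, giving 57.3% to 76.7% (stated 57% to 77%).

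All 18 cells reproduce within 1 point. Loss enters only as a smaller n, that is, as lost precision and not as possible bias. No persistence figure is stated, so there is none to reproduce.

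**3. How many men**

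Lost PrEP starters = 225 × acceptance × loss:

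| Acceptance | Starters | 10% loss | 20% loss |
|---|---|---|---|
| 33% | 74.2 | 7.4 | 14.9 |
| 50% | 112.5 | 11.2 | 22.5 |
| 67% | 150.8 | 15.1 | 30.2 |

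**4. Effect on Week 52 persistence**

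Let S be persistence among attenders (an assumption, 50% to 80%) and L the loss (10% or 20%, Section 7.2). Take four ACASI intervals with constant hazards and loss independent of earlier stopping.

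- Lost men censored: each interval contributes S^(1/4), so the estimate is S.
- Lost men counted as stopped: each interval contributes (1 − L)^(1/4) × S^(1/4), so the estimate is S × (1 − L).
- Difference: S × L.

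| S | Censored | Stopped, L = 10% | Stopped, L = 20% |
|---|---|---|---|
| 50% | 50% | 45% | 40% |
| 70% | 70% | 63% | 56% |
| 80% | 80% | 72% | 64% |

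The difference is 5 to 8 points at 10% loss and 10 to 16 points at 20% loss. If half of the lost men are captured later or behave like attenders, L is halved and the difference becomes 2.5 to 4 and 5 to 8 points.

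**5. Incarceration estimate**

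- 0.10 × 225 = 22.5 and 0.20 × 225 = 45, so the percentages imply about 23 to 45 men.
- 15/225 = 6.7% and 30/225 = 13.3%, so the counts imply lower percentages.
- 15/0.10 = 30/0.20 = 150, so the pair fits a base of 150, not 225.

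**The case against.** The strongest reply is that the protocol does not write out how lost men enter the analysis. Censoring rules often sit in the SAP, which is not at hand and could add one. That is fair as to the rule, but the event definition is fixed in the protocol with one trigger and one exception. An SAP that counted loss of supply as stopping would have to override that definition.

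Several stronger readings are tempting, and the objection defeats them:

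- A reader might infer that lost men are scored as still on PrEP. Kaplan-Meier does not do that. It removes them from the risk set and assumes they share the attenders' later hazard, so bias arises only if they stop more often. Loss of supply makes this likely but does not make it certain.
- A reader might infer that every lost or incarcerated man is missed. The exit and release provisions show otherwise.
- A reader might take S × (1 − L) as the true figure. It is a worst case. A man supplied at Week 39 who misses only Week 52 may still hold tablets near Week 52. If loss were spread evenly (an assumption), about a quarter would fall after Week 39. S = 70% would then give 0.70 × 0.925 = 64.8% or 0.70 × 0.85 = 59.5%, not 63% or 56%. Off-study PrEP use is also possible, and the protocol plans to test for off-study ARV use.
- A reader might say the bias exceeds the planned precision. At 10% loss the Table 3 half-widths are about 8 to 12 points, against at most 5 to 8 here, and that table concerns the adherence rate, not persistence.

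It also stands that Section 7.2 names acceptance and percentage adherence as the primary endpoints. Persistence is one of several primary analyses in an uncontrolled estimation study, and no hypothesis test depends on it.

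**Conclusion.** The concern holds for men with no later ACASI. Following the stated definition, and with censoring as the default, persistence tends to be overstated. The figures in step 4 are upper bounds: they rest on an assumed attender persistence, on the protocol's loss range applied to PrEP starters, and on every lost man being off drug by Week 52. Distortion of the subgroup curves is conditional on loss differing by group, which the protocol does not address.

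The incarceration mismatch is a separate and smaller error. A reader might infer that 23 to 45 is the intended count, but nothing in the protocol shows whether the count or the percentage is right.

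**What to change.** For analysis, define the discontinuation date as the earlier of:

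- (a) an ACASI-reported gap of 30 days or more; and
- (b) 30 days after the dispensed supply is exhausted with no further dispensing.

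Apply both within the 52-week follow-up and exclude clinician-instituted holds. Report incarceration separately so that its share of stopping is visible. Keep the ACASI-only rule as a sensitivity analysis.

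In Section 3.2.1, reconcile the count with the percentage for 225 participants and state the base used.

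The cost is wording in the protocol or SAP and some programming. No new data are needed: pharmacy dispensing records are kept under Section 4.4, tablets dispensed already feed the possession ratio in Section 7.3.1, and known incarceration is entered on case report forms under Section 3.2.1. The downside is that men who obtain PrEP elsewhere are counted as stopped, and reported persistence will be lower.

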2.2 Secondary Objectives

- To describe side effects, toxicities, risk compensation, and STIs among participants who initiate PrEP
- To describe patterns and attributes of PrEP initiation and adherence among participants (e.g., C4, substance use, sociocultural factors and incarceration)
- To measure changes in sexual risk taking behavior among study participants
- To describe reasons BMSM choose to initiate or decline PrEP
- To describe the number of HIV seroconversions, and to analyze viral characteristics (e.g., drug resistance) and the host response to infection in participants who become HIV-infected while on PrEP
- To characterize the participant perception of care and referral plans

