7.3.2 Secondary Analyses

Analyses for secondary objectives will be mostly descriptive. Line listings as well as summary descriptive statistics including means, medians, and proportions with 95% exact or asymptotic confidence intervals as appropriate at each visit, will be used for the following secondary objectives. Specifically,

- Use GEE or random effects models to describe longitudinal patterns and their correlates of PrEP initiation and adherence among participants (e.g.: C4, substance use, sociodemographics, sociocultural factors, risk practices and incarceration)
- To describe side effects and toxicities of PrEP among participants in the PrEP demonstration project. AEs will be tabulated, overall and by grade. For any reasonably common AEs (> 20 events), exploratory analyses will be conducted to assess correlates of the AE, including demographics and duration and patterns of PrEP use, within the limits imposed by the small expected number of events.
- Describe and produce summary plots for longitudinal changes in sexual risk-taking behavior among study participants
- List and summarize reasons BMSM choose to initiate or decline PrEP
- List and summarize HIV seroconversions and characteristics of the infection(s) (e.g., viral set point, drug resistance patterns) in participants who initiated PrEP
- Use Kappa-statistics to assess agreement of adherence under different measures.

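### The 30-day PrEP discontinuation rule does not exempt time in custody, when the study supplies no PrEP, so persistence and restart times mix unchosen gaps with participants' own stopping

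*Protocol*

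**What the plan says.** Protocol Section 7.3.1 measures persistence from PrEP start to discontinuation. Discontinuation means that a participant reports by ACASI that he did "miss the PrEP doses for 30 or more consecutive days, for reasons other than a medication hold instituted by a clinician". Two analyses rest on this event: "Kaplan-Meier plots will be used to characterize time to first discontinuation, as well as time to restarting PrEP among discontinuers", and "PrEP persistence times will be analyzed by multiplicative Andersen-Gill counting processes models".

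Protocol Section 3.2.1 says that enrolled men who are incarcerated "will not be followed while incarcerated, no data will be collected on them, and neither C4 nor PrEP provided". It adds that "once released, participants will be followed, if they wish, from the time of release until the originally scheduled Week 52 visit". It expects 15-30 participants, or 10% to 20%, to be incarcerated during follow-up, and it has known information about them recorded on case report forms.

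Section 7.2 includes men lost through incarceration in its assumed 10% to 20% loss to follow-up. Section 7.3.2 gives incarceration as an example correlate where it plans to "Use GEE or random effects models to describe longitudinal patterns and their correlates of PrEP initiation and adherence among participants". Nothing in the protocol says how custody time enters the persistence or restart analyses.

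**The concern.** The rule already removes one kind of gap that the participant did not choose, the clinician's hold. Incarceration is the other such gap that the protocol foresees, and during it the study supplies no drug. It is not a clinician's hold, so the exemption does not reach it.

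Three analyses under the Section 7.3.1 heading are affected:

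- Time to first discontinuation gains events that are not decisions to stop.
- Time to restart for these men cannot end before release. After 60 days off PrEP, Sections 5.5 and 5.6 also require eligibility to be re-confirmed first. The restart curve then partly describes release dates and re-screening.
- The Andersen-Gill analysis counts recurrent events, so each qualifying custody gap can add one.

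The study is meant to show how well these men stay on PrEP once they choose it. A persistence figure that includes gaps in supply understates that. An analysis plan that follows the protocol's rule reproduces the problem, and one that departs from it contradicts the protocol.

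**Working it through.** **Inputs from the protocol.** N = 225 and acceptance of 33%, 50% or 67% (Section 7.2); 15-30 men or 10-20% incarcerated (Section 3.2.1).

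**Assumptions.** Let c be the proportion of initiators incarcerated while on PrEP, taken equal to the proportion in the whole cohort. Let f be the share of those men who are held for 30 or more days, return, and report the gap by ACASI. The protocol gives no value for f, so 0.25 to 1 is shown. True persistence S is set at 70% for illustration. Incarceration is taken as independent of voluntary stopping.

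**1. The plan's own precision, as a yardstick.** At 50% acceptance, 10% loss and 67% adherence, n = 225 × 0.50 × 0.90 = 101.25. The normal-approximation interval is 0.67 ± 1.96 × √(0.67 × 0.33 / 101.25) = 0.67 ± 0.092, or 57.8% to 76.2%. This reproduces the printed 58%-76%, with a half-width of about 9 points.

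**2. The two incarceration figures.** 15/225 = 6.7% and 30/225 = 13.3%, whereas 10% and 20% of 225 are 22.5 and 45 men. A count of 15-30 is 10-20% of 150, not of 225. The two figures do not agree, so both are carried forward.

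**3. Initiators affected.** At 50% acceptance there are 225 × 0.50 = 112.5 initiators.

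| Basis | c | Incarcerated initiators (112.5 × c) | Meeting the rule, f = 0.25 to 1 |
|---|---|---|---|
| 15 men | 6.7% | 7.5 | 1.9 to 7.5 |
| 30 men | 13.3% | 15 | 3.8 to 15 |
| 10% | 10% | 11.25 | 2.8 to 11.25 |
| 20% | 20% | 22.5 | 5.6 to 22.5 |

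At 33% acceptance (about 74 initiators), the incarcerated initiators number about 5-10 on the count and 7-15 on the percentages. At 67% (about 151) they number about 10-20 and 15-30.

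**4. Effect on persistence.** Under the literal rule, observed persistence = S × (1 − c × f), so the fall is S × c × f. It is smaller than c × f because some of these men would have stopped anyway.

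- Count, smallest: 70 × 0.067 × 0.25 = 1.2 points.
- Count, largest: 70 × 0.133 × 1 = 9.3 points.
- Percentages, smallest: 70 × 0.10 × 0.25 = 1.75 points.
- Percentages, largest: 70 × 0.20 × 1 = 14 points.

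**5. Association created by the definition.** Suppose incarceration has no effect on voluntary stopping, which occurs in a proportion b of men. The risk ratio for discontinuation by incarceration is then [f + (1 − f) × b] / b. With b = 0.33 it is 0.4975/0.33 = 1.5 at f = 0.25 and 1/0.33 = 3.0 at f = 1. With b = 0.50 it runs from 1.25 to 2.0. This applies only if someone relates this discontinuation event to incarceration.

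**The case against.** The strongest reply is that an all-cause measure is legitimate. A custody gap is a real loss of PrEP coverage, and an uncontrolled demonstration project may want to count it. That makes the literal rule worth reporting. It does not explain why the rule excludes a clinician's hold, which is also a loss of coverage, and keeps custody. As written, the measure is neither all-cause nor limited to the participant's own stopping.

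A second reply is that the trigger is uncertain. The ACASI questions are not in the protocol, and a man may not report unsupplied doses as missed. This stands, and it is one reason why f is a range.

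Several stronger readings are tempting but not supported:

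- A reader might infer that the plan tests incarceration as a correlate of stopping and so finds an association that is true by definition. Section 7.3.1 splits its curves by age, education and risk group and lists no covariates for the Andersen-Gill model. Incarceration is named in Sections 2.2 and 7.3.2 for initiation and adherence, not for the 30-day event.
- A reader might infer that men who never return are coded the opposite way, as still persistent. The protocol states no censoring rule. A censored man leaves the risk set and is not counted as persistent.
- A reader might take the top of the range as the expected bias. That requires every incarcerated initiator to be held for 30 or more days, return and report the gap, and it ignores the lower count of 15-30.
- A reader might call this a flaw in a primary endpoint. The endpoints sized in Section 7.2 are the acceptance rate and the adherence percentage. Persistence is one of several analyses under Section 7.3.1.

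**Conclusion.** The point holds with limited scope. Followed literally, Section 7.3.1 counts a custody gap of 30 or more days as discontinuation when the man returns and reports it, although Section 3.2.1 has the study supply no PrEP in that time. No section exempts, censors or separates it.

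If the target is participants' own stopping, the direction is clear: persistence is understated. The size is not established. Under the stated assumptions it is about 1 to 9 points on the count and about 2 to 14 on the percentages, against a planned half-width of about 9 points for adherence. If men likely to be incarcerated also stop voluntarily more often, fewer would be on PrEP when custody begins and the shift would be smaller.

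Any analysis that did relate this event to incarceration would carry a partly built-in association, but the protocol does not list one. Severity is moderate: there is no treatment comparison or decision threshold, and either coding can be produced if custody dates are recorded.

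**What to change.** In Protocol Section 7.3.1, extend the exemption beyond clinician holds to any period of incarceration in which study product was not provided. Then:

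- Take custody days out of the time at risk for discontinuation and for restart. Stop the clock at incarceration and let the man re-enter at release, using the incarceration case report form.
- Report incarceration-related interruptions as a separate reason, with their number and length.
- Give the literal rule, with custody gaps counted as discontinuation, as a sensitivity analysis.
- Reconcile 15-30 participants with 10% to 20% of 225 in Section 3.2.1.

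The cost is a sentence or two of text and some extra programming. The case report form must hold start and release dates; the protocol does not say whether it does. The main estimate would no longer count custody as lost coverage, which the sensitivity analysis shows. Removing custody time also assumes that incarceration is unrelated to the tendency to stop, and the report should say so. Clinical management does not change. The rule should be set before the persistence data are examined.
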